### 6.2.1 Screening Evaluation

#### Consenting Procedure

If the patient is interested and referred by the physician, the Project Manager or other study team member will approach or call interested patients prior to surgery to

explain the protocol, answer questions, determine eligibility, and discuss informed consent. After making sure the patient clearly understands the study procedures and agrees to follow them, the patient will be asked to sign the informed consent form electronically (via REDCap) or in person. Either a hard copy or email attachment of the informed consent document will be given to the participant, and the original copy will be kept in the participant's file. Each participant will be asked to separately agree to be videotaped for the study, which will not affect their ability to participate. If they do consent to be videotaped, they are told in the consent form that they can ask not to be included in the filming or withdraw their consent to be videotaped at any time. These videos are focused on the interventionist for the sole purpose of increasing treatment fidelity. We will also let participants know at the time of consent that it is their choice whether or not visitors remain in the room during the intervention and ask if they have a preference.

### **Screening**

Screening evaluations will begin once a patient is scheduled for a consultation related to receiving surgery for a suspected gynecologic malignancy. The allowable range of time for screening is up to one year prior to study entry and baseline assessment. Electronic medical records of patients planning to receive chemotherapy will be reviewed by a study team member to identify potential patients that meet enrollment criteria. This screening will consist of:

- Review of medical history
- Review of treatment plan

We will approach patients either in person or remotely (e.g., telephone, myWakeHealth, mail) regarding their interest in study participation. For patients interested in the study, research staff will verify eligibility through patient interview regarding medical history.

#### **6.2.2 Enrollment, Baseline, and/or Randomization**

##### **Enrollment**

Enrollment is defined as the randomization date or as the date all of the screening criteria are met and the individual agrees to participate.

##### **Registration Procedures**

All patients entered on any CCCWFU trial, whether treatment, companion, or cancer control trial, **must** be registered with the CCCWFU Protocol Registrar or entered into Oncology Research Information System (ORIS) Screening Log within 24 hours of Informed Consent. Patients **must** be registered prior to the initiation of treatment.

The following steps must be performed in order to ensure prompt registration:

1. Complete the Eligibility Checklist (Appendix K)
2. Complete the Protocol Registration Form (Appendix L)

3. Alert the Cancer Center registrar by phone, *and then* send the signed Informed Consent Form, Eligibility Checklist and Protocol Registration Form to the registrar, either by fax or e-mail.
  
4. Fax/e-mail ALL eligibility source documents with registration. Patients **will not** be registered without all required supporting documents.

Note: If labs were performed at an outside institution, provide a printout of the results. Ensure that the most recent lab values are sent.

To complete the registration process, the Registrar will:

- assign a patient study number
- other appropriate actions
- register the patient on the study

### **Baseline Assessments**

For participants who have successfully been screened for eligibility and are enrolled into the study, baseline assessments will be performed. The baseline assessment may be completed within two weeks prior to surgery.

- *Assessment Completion/Retention.* Percent completion of planned standard and daily assessments.
- *Pain.* The Patient Reported Outcomes Measurement Information System (PROMIS) measure of pain of intensity (i.e., How would you rate your pain on average?), which has been adapted for assessing pain on a numeric rating scale from 0 (no pain) to 10 (worst imaginable pain) “in the last day,” is the proposed primary outcome (at 2 weeks) for the future larger clinical trial that will be informed by the current study. Patient-reported pain is considered the ‘gold standard’ for pain assessment since pain is a subjective experience and PROMIS is supported by the NCCIH and National Cancer Institute. Pain interference, the affective dimension of pain, and analgesic use will be assessed using 9 patient-reported items. *Pain interference* will also be assessed with a PROMIS measure (6-items). The *affective dimension of pain* will be assessed with one item on a scale from 0 (not bad at all) to 10 (the most unpleasant feeling possible for me). *Analgesic use* in the past 24-hours will be tracked daily for one week before and one week post-surgery (postoperative day 1 to 8; day added since participants may report information from the prior day) and converted to a cumulative analgesic consumption score for analysis (2-items). We will also ask participants if they are taking any analgesic medication postoperatively.
- *Sleep Disturbance* will be assessed with a PROMIS Sleep Disturbance short-form (8-items) adapted for daily use.
- *Psychological Distress.* The PROMIS Depression (8-item) & Anxiety (7-item) adapted short-forms will be used to assess psychological distress “in the last day.”

- *Pain Self-Efficacy* will be assessed with the pain management subscale of the Chronic Pain Self-Efficacy Scale, which has been used postoperatively (5-items).
- Daily Symptoms will be assessed for up to one week before surgery and week after surgery starting on postoperative day 1 (or as soon as feasible) using 4 items on pain (2), disturbed sleep, and distress. The same adapted PROMIS pain intensity item will be asked and sleep disturbance and psychological distress items will be used from the MD Anderson Symptom Inventory (MDASI), which asks about each symptom at “its worst” in the past 24 hours from the MDASI designed to be implemented daily and used perioperatively.
- *Sleep Disturbance* will also be assessed with *actigraphy*, a non-intrusive alternative to the traditional polysomnography when monitoring sleep. The Activwatch Spectrum model actigraph will be worn for up to 1 week before surgery and one week after surgery starting on postoperative day 1. This watch-like device measures rest/activity patterns in a natural setting, and provides summary measures of daily sleep activity. Sleep disturbance will be defined as a daily ratio of circadian disruption (the ratio of nighttime activity to daytime activity; higher scores show greater circadian disruptions). A similar device and the same ratio has been used in patients perioperatively. Participants will also self-report the time spent napping and their bed and rising times daily.
- *Demographic Factors.* Age, race/ethnicity, marital status, education level, ability to pay for the basics, distance travelled for care, medical history, previous use of mind-body practices, baseline level of mindfulness, and internet access will be self-reported at baseline.
- *Clinical Factors.* Cancer site, type of surgery stratified by risk, treating physician, date diagnosed, other cancer treatments, comorbidities, height, weight, prescription medications for pain, sleep, depressive symptoms, and anxiety will be abstracted from medical charts at baseline.

### Randomization

Randomization will occur the same day that screening is confirmed. Instructions for completing the intervention will begin at the same visit.

#### 6.2.3 Blinding

- Participants will be told that both groups offer programs to support their experience in coping with surgery to match efficacy expectations.
- The study team member collecting outcome assessments will be blinded to group assignment.
- A complete description of each study arm will be presented to participants upon their completion of all study measures.

#### 6.2.4 Follow-up Visits

The timing of study assessments is summarized in Table 1. Postoperative day 1 assessments may be completed within 3 days after surgery. The two-week and 4-week assessments can be timed with in-person follow-up visits, which may be

scheduled within a week of the scheduled assessment. Descriptions of additional measures not assessed at baseline include:

- *Adherence.* Completion of the videoconference session
- *Interventionist Communication.* Any additional contact with the interventionists.
- *Intervention Home Practice.* Use of the self-directed intervention (time and duration) will be measured daily for up to one week before and one week after surgery as assessed in another yoga study. Self-reported time of practice will also be assessed retrospectively (in the past week) at postoperative weeks 2 and 4.
- *Acute Adverse Events.* Participants will also be asked to complete two Visual Analogue Scale items assessing pain intensity and psychological distress daily with the instructions to report their experience “right now,” immediately before and after the intervention to detect any acute adverse events.
- *Expected Benefit.* The HEAL Treatment Expectancy measure 6-items) will assess expected benefit of the intervention following the videoconference session.
- *Daily Symptoms* will be assessed for up to one before surgery and week after surgery starting on postoperative day 1 (or as soon as feasible) for 8 days (since participants may report information from the prior day) using 3 items on pain, disturbed sleep, and distress. The same PROMIS pain intensity item will be asked and sleep disturbance and psychological distress items will be used from the MDASI, which asks about each symptom at “its worst” in the past 24 hours from the MDASI designed to be implemented daily and used perioperatively.
- *Sleep Disturbance* will also be assessed with *actigraphy*, a non-intrusive alternative to the traditional polysomnography when monitoring sleep. The Actiwatch Spectrum model actigraph will be worn for up to 1 week before surgery and one week after surgery starting on postoperative day 1. This watch-like device measures rest/activity patterns in a natural setting, and provides summary measures of daily sleep activity. Sleep disturbance will be defined as a daily ratio of circadian disruption (the ratio of nighttime activity to daytime activity; higher scores show greater circadian disruptions). A similar device and the same ratio has been used in patients perioperatively. Participants will also self-report their bed and rising times daily.
- *Patient Provider Connection* will be measured with a 7-item short-form from the Healing Encounters and Attitudes Lists (HEAL) at the 4-week follow-up visit.
- *Clinical Factors.* Medications prescribed for pain, length of stay, any complications experienced, and other cancer treatments, will also be abstracted four weeks post-surgery.

### **6.2.5 Completion/Final Evaluation**

Assessments to be performed at the participant’s final visit are described in the prior section. Participants who discontinue study the intervention early will require no specific evaluations. The reason for discontinuation will be documented. We will contact participants to obtain follow-up data remotely if they discontinue participation due to change in treatment location. Patients terminated from the study will undergo no further monitoring once they have stopped the study intervention.

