## 6.2 Description of Evaluations

To minimize burden, assessments, and interviews will be implemented while patients are at home or already on site for standard care. At the time of enrollment, participants will be provided a tablet computer to borrow for the study (unless they already have a comparable device that they prefer) and receive training on completing questionnaires either online or by telephone, similar to a training successfully implemented in a study of symptom monitoring in this patient population. This prior study suggested that alternate data collection methods such as automated telephone calls may increase adherence to web-based symptom reporting. Patient-reported questionnaires will be conducted at four time points: before surgery (baseline), one day after surgery, two weeks after surgery and 4 weeks after surgery.

We are most interested in assessing and then effectively managing acute within one week following surgery when pain is likely to be highest, and how pain management during this period may ultimately impact longer-term pain. Daily diaries are one method for measuring an experience in a participant's natural setting with low patient burden. Thus, participants will also be asked to complete daily surveys of outcomes and adherence to home practice of the intervention via REDCap and wear a wrist actigraphy device for up to one week before and one week following surgery. REDCap is a flexible electronic data capture system offered by the Wake Forest CTSI that will verify the date and time of assessments implemented via the internet, telephone, or paper. Our team has piloted the use of REDCap for implementing daily assessments during our ongoing study. Women with gynecologic malignancies have demonstrated reasonable compliance (86%) with electronic diary assessment and daily assessments after gynecologic oncology surgery (68% compliance). Participants will be prompted to complete the surveys (3-5 minutes) at approximately 6:00pm each evening and can complete the survey any time before they go to sleep. A paper guide with response options for the questionnaire will be provided to improve comprehension over the telephone. Participants will also be given a wrist actigraphy device and instructions for its use during this same time period.

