In addition, demographic data will be patient-reported at baseline, medical records will be reviewed to obtain clinical data, treatment fidelity observed at the videoconference intervention session, and an interview conducted at a follow-up clinic visit or by telephone. Participants will be compensated up to \$100 total for completing study assessments. We will also track recruitment, adherence to the videoconference intervention, any other contact with interventionists, completion of assessments, and any adverse events that may occur. Those who decline participation or drop out of the study will be asked for feedback about their choices.

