## **8. INTERVENTION DISCONTINUATION**

The intervention will be discontinued for a participant if: (1) the intervention is associated with an adverse effect for a specific participant (i.e., participant does not tolerate the intervention), (2) the participant no longer is interested or willing to receive the intervention or participate in the study, or (3) the participant's healthcare provider no longer recommends that the patient receive the intervention for medical reasons. The IMC and the principal investigator will review cases upon occurrence for discontinuation of intervention.

This study will be stopped prior to its completion if: (1) the intervention is associated with adverse effects that call into question the safety of the intervention; (2) difficulty in study recruitment or retention will significantly impact the ability to evaluate the study endpoints; (3) any new information becomes available during the trial that necessitates stopping the trial; or (4) other situations occur that might warrant stopping the trial. The PI will include an assessment of futility in the annual progress report to NIH and will consult with the study monitors to assess the impact of significant data loss due to problems in recruitment, retention, or data collection.

Participants will be followed with their permission if the study is discontinued. The duration of follow-up will be length of the proposed study. We will continue to document adverse events during the follow-up period.

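### Section 6.2.5, read literally, lets staff stop Week-2 and Week-4 data collection when a participant stops the intervention, contrary to the plan's own analysis aims and to the detriment of its main success measure

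*Combined protocol and SAP*

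**What the plan says.** **Section 6.2.5** has three relevant sentences.
- On people who stop the intervention: "Participants who discontinue study the intervention early will require no specific evaluations".
- On people who leave because they move: "We will contact participants to obtain follow-up data remotely if they discontinue participation due to change in treatment location".
- On people terminated from the study: "Patients terminated from the study will undergo no further monitoring once they have stopped the study intervention".

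It also says that the reason for discontinuing is recorded.

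**Section 8** lists as one reason to discontinue the intervention that "the participant no longer is interested or willing to receive the intervention or participate in the study". Its follow-up commitment concerns closure of the whole trial: "Participants will be followed with their permission if the study is discontinued".

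**Section 6.2** sets the questionnaire schedule without reference to intervention use: "Patient-reported questionnaires will be conducted at four time points". Participants "receive training on completing questionnaires either online or by telephone". The only contact it specifies with people who leave is a request for their views: "Those who decline participation or drop out of the study will be asked for feedback about their choices".

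**Sections 1.1, 9.2 and 9.6** make Week-2 retention the main sign that the pilot succeeded, measure it by completion of the 2-week visit, and compare it with 70%. Section 9.2 plans on 25 retained and 6 lost out of 31.

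**The concern.** Stopping the intervention and leaving the study are different events, and a feasibility trial needs to count them separately. The first bears on adherence, the second on retention. Section 6.2.5 sets no data-collection requirement for the first group, and the text reviewed nowhere states that their scheduled assessments go on. A coordinator working from 6.2.5 could reasonably conclude that no further questionnaires are due.

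A participant who gave up the video or the diary but would have answered a Week-2 questionnaire would then be recorded as not retained. Retention would partly measure adherence a second time. The Week-2 and Week-4 pain, sleep and distress data, wanted mainly to estimate standard deviations for the next trial, would be missing for reasons that are unlikely to be random. Section 8 lists those reasons as an adverse effect, loss of interest or willingness, and a provider's advice. Later adverse-event inquiry could lapse as well: Section 7.5 follows events while participants are enrolled, and whether a stopper remains enrolled is what the text leaves open.

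**Working it through.** **Step 1. The passages side by side.**

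| Place | What it implies for someone who stops the intervention |
|---|---|
| 6.2.5, first rule | No particular evaluation is required |
| 6.2.5, relocation sentence | Follow-up data are promised for one reason, but the sentence concerns people leaving the study |
| 6.2.5, termination sentence | Monitoring ends, but for people terminated from the study; the end point is tied to stopping the intervention |
| 8, second criterion | Unwillingness to receive the intervention and unwillingness to be in the study share one criterion; nothing on data collection |
| 6.1 and 6.2 | Questionnaires are scheduled by time point, not by intervention use |
| 9.3 | Invokes intention-to-treat and limiting missing data; points to an earlier specification that does not mention stoppers |
| 9.5.1 and 9.6 | Adherence and retention are separate measures; non-adherent participants and drop-outs are named separately |
| 9.6 | Relates adherence to change in the outcomes, which needs outcomes from people with little or no practice |

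The analysis sections presuppose data from people who stop. Section 6.2.5 does not require those data to be collected. That is the conflict to be reconciled.

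**Step 2. Reproduce the plan's figure.** Inputs from 9.2: n = 31, observed retention 80%, one-sided 95% limit. The normal-approximation lower limit is p − 1.645 × √(p(1 − p)/n).

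0.80 − 1.645 × √(0.80 × 0.20/31) = 0.80 − 0.118 = 0.682, the stated 68.2%.

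**Step 3. Effect of each reachable stopper who is not asked.** Assume that all 31 stay in the denominator and that these people are additional to the six planned losses. Each costs 1/31 = 3.2 points.

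| Not asked | Week-2 retention | Lower limit, plan's formula | Lower limit, exact (Clopper-Pearson) |
|---|---|---|---|
| 0 | 25/31 = 80.6% | 69.0% | 65.3% |
| 1 | 24/31 = 77.4% | 65.1% | 61.7% |
| 3 | 22/31 = 71.0% | 57.6% | 54.8% |
| 4 | 21/31 = 67.7% | 53.9% | 51.5% |

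By the plan's formula, one such loss takes the limit below the 68% cited in 9.2. Four take the observed rate below 70%. By the exact method the limit is already below 68% at 25/31, so the 68% statement depends on the approximation.

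**Step 4. Relax the two assumptions.**
- If the six planned losses already include reachable stoppers, Step 3 counts them twice. Asking them would then raise retention above the planned level; one recovered gives 26/31 = 83.9%.
- If stoppers are removed from the denominator, the direction can change. Dropping one reachable stopper from both counts gives 24/30 = 80.0%. Dropping one of the six who would be lost anyway gives 25/30 = 83.3%. Section 9.6 does not fix the denominator.

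**Step 5. Range for the unknown stopping rate.** The documents give none. As an assumption, let 0% to 20% of participants who would complete Week 2 if asked stop early and not be asked, with the chance of completing if asked set at 80% (the plan's figure) or 90% (assumed). The binomial probability of observing at least 25 of 31 is:

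| Stop and not asked | 0% | 5% | 10% | 15% | 20% |
|---|---|---|---|---|---|
| Complete if asked: 80% | 0.57 | 0.36 | 0.19 | 0.09 | 0.04 |
| Complete if asked: 90% | 0.97 | 0.85 | 0.63 | 0.38 | 0.19 |

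These values show sensitivity only; they are not a forecast.

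**The case against.** The strongest case is that 6.2.5 means something narrower. It sits under the final evaluation, and its rule for stoppers follows a sentence about final-visit assessments, so the natural sense may be only that no extra exit visit is needed. The scheduled questionnaires in 6.1 and 6.2 do not depend on intervention use, and remote completion is routine. Week 4 is assessed although home practice is optional after two weeks (5.1). Sections 9.3 and 9.6 point to continued assessment. All of this stands as evidence of likely intent. It does not supply the missing instruction, and the consent form (Appendix A, cited in 4.3), which might, is not in the text reviewed.

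A reader might also infer more than the documents support:
- *That Section 8 ends data collection.* It does not. It joins two kinds of unwillingness in one criterion and is silent on individual follow-up.
- *That the relocation and termination sentences are rules for intervention stoppers.* They concern people leaving the study. They add to the ambiguity because 6.2.5 gives stoppers no parallel statement.
- *That an adverse effect causing a stop would go unrecorded.* The reason is documented (6.2.5), the principal investigator and monitoring committee review the case (8), and complications are abstracted from charts at four weeks (6.2.4). Only later inquiry is in doubt.
- *That the error can only understate retention.* That needs all randomised participants in the denominator, which 9.6 does not state.
- *That falling below 70% stops the programme.* Section 9.2 words the feasibility concern jointly with recruitment and adherence, and tentatively.

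**Conclusion.** The point holds as an unresolved conflict in the wording. The text does not show that follow-up of stoppers is meant to end; it permits staff to end it, while the analysis sections need the data. Continued assessment is probably intended, which is a reason to say so.

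The size is 3.2 points of Week-2 retention for each reachable stopper who is not asked. This is conditional on the literal reading being followed and on all 31 remaining in the denominator. The number affected cannot be derived from the documents and may already lie within the six planned losses, so the counts are illustrative. The sample size and the plan's 68.2% figure are not in question. The issue is worth correcting because it touches the main success indicator and the correction is cheap. Confidence is medium, given the plausible narrower reading and the unseen consent form.

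**What to change.** 1. In 6.2.5 and 8, reconcile the passages by defining two separate states: stopped the intervention, and withdrew from data collection.
2. State that a participant in the first state is still asked for the scheduled Week-2 and Week-4 questionnaires and the adverse-event inquiry, remotely if needed, unless she withdraws from data collection.
3. In 9.6, calculate retention as Week-2 completion, in person or remote, among all randomised participants regardless of intervention status. This also settles the denominator.
4. Check that the consent form says the same.

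The cost is a short wording amendment and a few extra contacts with people who have stopped. Online and telephone completion and recording of the reason for discontinuing are already in the protocol, so no new procedure is needed.
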